### **8.2.4 Clinical Safety Laboratory Assessments**

- See Appendix 2 (Section 10.2) for the list of clinical laboratory tests to be performed and to the SoA (Section 1.3) for the timing and frequency.
- Abnormal laboratories will be classified according to the NCI CTCAE, version 5.0.
- The Investigator must review the laboratory report, document this review, and record any clinically significant changes occurring during the study as an AE. If a laboratory finding is abnormal but not clinically significant (NCS) at baseline, postbaseline laboratory abnormalities will be reported as an AE only if there is worsening compared to baseline.
- The laboratory reports must be filed with the source documents.
- Abnormal laboratory findings associated with the underlying disease are not considered clinically significant unless documented by the Investigator.
- All laboratory tests with values considered clinically significantly abnormal during participation in the study should be repeated until the values return to normal or baseline or are no longer considered clinically significant by the Investigator or medical monitor.
  - If such values do not return to normal/baseline within a period judged reasonable by the Investigator, the aetiology should be identified, and the Sponsor notified.

- All protocol-required laboratory tests, as defined in Appendix 2 (Section 10.2), must be conducted in accordance with the laboratory manual and the SoA (Section 1.3).
- If laboratory values from non-protocol specified laboratory tests performed at the institution's local laboratory require a change in subject management or are considered clinically significant by the Investigator (e.g., SAE or AE or dose modification), then the results must be recorded.

### 8.2.5 Performance Status

#### ECOG Performance Status (Solid Tumours Cohort)

The Eastern Cooperative Oncology Group (ECOG) Performance Status will be used to assess subject's performance status ([Table 2](#)).

**Table 2: Eastern Cooperative Oncology Group (ECOG) Performance Status**

Grade	ECOG
0	Fully active, able to carry on all pre-disease performance without restriction
1	Restricted in physically strenuous activity but ambulatory and able to carry out work of a light or sedentary nature, e.g., light housework, office work
2	Ambulatory and capable of all self-care but unable to carry out any work activities. Up and about more than 50% of waking hours
3	Capable of only limited self-care, confined to bed or chair more than 50% of waking hours
4	Completely disabled. Cannot carry on any self-care. Totally confined to bed or chair
5	Dead

#### Karnofsky Performance Status (Haematologic malignancies Cohort)

Karnofsky performance status scale will be performed at screening to assess subject's functional impairment, ranging from 100 to 0, in increments of 10, where 100 is normal health and 0 is death ([Table 3](#)). To be eligible to participate in this study, subjects must have a Karnofsky performance status of  $\geq 60\%$ . This scale was shown to be valid in assessing geriatric population ([Crooks, 1991](#)).

**Table 3: Karnofsky Performance Status**

Able to carry on normal activity and to work; no special care needed.	100	Normal; no complaints; no evidence of disease.
	90	Able to carry on normal activity; minor signs or symptoms of disease.
	80	Normal activity with effort; some signs or symptoms of disease.
Unable to work; able to live at home and care for most personal needs; varying amount of assistance needed.	70	Cares for self; unable to carry on normal activity or to do active work.
	60	Requires occasional assistance but is able to care for most of their personal needs.
	50	Requires considerable assistance and frequent medical care.
Unable to care for self; requires equivalent of institutional or hospital care; disease may be progressing rapidly.	40	Disabled; requires special care and assistance.
	30	Severely disabled; hospital admission is indicated although death not imminent.
	20	Very sick; hospital admission necessary; active supportive treatment necessary.
	10	Moribund; fatal processes progressing rapidly.
	0	Dead

### 8.3 ADVERSE EVENTS (AEs), SERIOUS ADVERSE EVENTS (SAEs), AND OTHER SAFETY REPORTING

AEs will be classified according to the NCI CTCAE, version 5.0.

The definitions of adverse events (AEs) and serious adverse events (SAEs) can be found in Appendix 3 (Section 10.3).

AEs will be reported by the subject (or, when appropriate, by a caregiver, surrogate, or the subject's legally authorized representative).

The Investigator and any qualified designees are responsible for detecting, documenting, and recording events that meet the definition of an AE or SAE and remain responsible for following up AEs that are serious, considered related to the study intervention or study procedures, or that caused the subject to discontinue the study intervention (see Section 7).

The method of recording, evaluating, and assessing causality of AEs and SAEs and the procedures for completing and transmitting SAE reports are provided in Appendix 3 (Section 10.3).

### 8.3.1 Time Period and Frequency for Collecting AE and SAE Information

All AEs and SAEs will be collected from the signing of the ICF until the follow-up visit at the time points specified in the SoA (Section 1.3).

Table 4 below summarizes the different observation periods for AEs, and SAEs.

**Table 4: Adverse Event Reporting Periods and Reporting Timelines to the Sponsor**

Type of Event	Adverse Event	Serious Adverse Event
Reporting period	From first dose of the study intervention until 30 days after the last dose of study intervention discontinued or before initiation of subsequent anticancer therapies, whichever comes first.	From consent until 30 days after the last dose of study intervention discontinued for all SAEs, and any time after that window if the SAEs are believed to be related to study intervention.
Reporting Timelines to the Sponsor	Entered the clinical database on an ongoing basis.	Within 24 hours.

All SAEs will be recorded and reported to the Sponsor or designee immediately and under no circumstance should this exceed 24 hours, as indicated in Appendix 3 (Section 10.3). The Investigator will submit any updated SAE data to the Sponsor within 24 hours of it being available.

Medical occurrences that begin before the start of the study intervention but after obtaining informed consent will be recorded on the Medical History section of the eCRF not the AE section, unless the medical occurrence is an SAE.

The Investigator is responsible for ensuring that all AEs are properly captured in the subject's medical records and reported in the eCRF.

Investigators are not obligated to actively seek information on AEs or SAEs after conclusion of the study participation. However, if the Investigator learns of any SAE, including a death, at any time after a subject has been discharged from the study, and he/she considers the event to be reasonably related to the study intervention or study participation, the Investigator must promptly notify the Sponsor.

### 8.3.2 Method of Detecting AEs and SAEs

Care will be taken not to introduce bias when detecting AEs and/or SAEs. Open-ended and non-leading verbal questioning of the subject is the preferred method to inquire about AE occurrences.

### 8.3.3 Follow-up of AEs and SAEs

After the initial AE/SAE report, the Investigator is required to proactively follow each subject at subsequent visits/contacts. All SAEs will be followed until resolution, stabilization, the event is otherwise explained, or the subject is lost to follow-up (as defined in Section 7.4). Further information on follow-up procedures is provided in Appendix 3 (Section 10.3).

### 8.3.4 Regulatory Reporting Requirements for SAEs

- Prompt notification by the Investigator to the Sponsor of an SAE is essential so that legal obligations and ethical responsibilities towards the safety of subjects and the safety of a study intervention under clinical investigation are met.
- The Sponsor has a legal responsibility to notify both the local regulatory authority and other regulatory agencies about the safety of a study intervention under clinical investigation. The Sponsor will comply with country-specific regulatory requirements relating to safety reporting to the regulatory authority, HREC, and Investigators.
- An Investigator who receives an Investigator safety report describing an SAE or other specific safety information (e.g., summary or listing of SAEs) from the Sponsor will review and then file it along with the IB and will notify the HREC, if appropriate according to local requirements.

### 8.3.5 Pregnancy

- Details of all pregnancies in female subjects will be collected as outlined in Appendix 4 (Section 10.4).
- If a pregnancy is reported, the Investigator will record pregnancy information on the appropriate form and submit it to the Sponsor within 24 hours of learning of the female subject pregnancy.
- While pregnancy itself is not considered to be an AE or SAE, any pregnancy complication or elective termination of a pregnancy for medical reasons will be reported as an AE or SAE.
- Abnormal pregnancy outcomes (e.g., spontaneous abortion, foetal death, stillbirth, congenital anomalies, ectopic pregnancy) are considered SAEs and will be reported.
- The subject will be followed to determine the outcome of the pregnancy. The Investigator will collect follow-up information on the subject and the neonate, and the information will be forwarded to the Sponsor.
- Any post-study pregnancy-related SAE considered reasonably related to the study intervention by the Investigator will be reported to the Sponsor as described in Section 8.3.4. While the Investigator is not obligated to actively seek this information in former study subjects, he or she may learn of an SAE through spontaneous reporting.
- Any female subject who becomes pregnant while participating in the study will discontinue study intervention or be withdrawn from the study.

### 8.3.6 Disease Progression

Clinical signs or symptoms associated with progression of underlying malignancy are not reported as AEs if they are clearly consistent with the suspected progression of the underlying malignancy. Hospitalization **solely** due to the progression of underlying malignancy should NOT be reported as an SAE. Clinical symptoms of progression may be reported as AEs if the symptom cannot be determined as exclusively due to the progression of the underlying malignancy or does not fit the expected pattern of progression for the disease under study. The site should report clinical signs/symptoms that have met the SAE definition within 24 hours of

learning the event if the aetiology is not clear at the time of the onset. If the subsequent workup has revealed that the reported event is associated with progression of underlying malignancy, the follow-up information should be submitted, and event term should be updated to the cause that led to the hospitalization instead of disease progression. For example, if a subject is hospitalized with shortness of breath that is determined to be associated with worsening of pleural effusion during the subsequent workup, pleural effusion could be used an event term instead of disease progression. SAE that has been reported should not be deleted from the database if the event is determined to be associated with disease progression with subsequent workups.

If there is any uncertainty about an AE being due only to the disease under study, it should be reported as an AE or SAE.

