### Non-haematologic:

1.  $\geq$  Grade 3 non-haematologic toxicity, except for the following Grade 3 events that are considered either not an adverse event or events that could be managed with standard of care:
  - a) Grade 3 inflammatory reaction attributed to a local anti-tumour response (e.g., inflammatory reaction such as pain, irritation, or localized rash at sites of metastatic disease, lymph nodes, etc.).
  - b) Grade 3 fatigue lasting  $\leq 3$  days.
  - c) Grade 3 diarrhea, nausea, or vomiting lasting  $\leq 3$  days without or with use of anti-emetics or anti-diarrheals per standard of care.
  - d) Grade 3 rash and/or pruritis without use of corticosteroids or anti-inflammatory agents per standard of care.

2. Any Grade 3 or Grade 4 non-haematologic laboratory value if:
  - a) Clinically significant medical intervention is required to treat the subject and does not resolve within 72 hours, or
  - b) Potential drug-induced liver toxicities with laboratory parameters as described below
    - $\geq$  Grade 3 and above elevation in ALT or AST if an alternative explanation other than the study intervention is not available.
    - $\geq$  Grade 3 and above elevation of total bilirubin of any duration if an alternative explanation other than the study intervention is not available.
    - Grade 2 elevation AST/ALT with concurrent elevation of total bilirubin  $>2 \times$ ULN or INR  $>1.5 \times$ ULN if an alternative explanation other than the study intervention is not available.

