## 10.6 APPENDIX 6: MODIFIED RECIST v1.1 FOR IMMUNE-BASED THERAPEUTICS

Immunotherapeutics may result in infiltration of immune cells leading to transient increase in the measured size of a target lesion, or undetectable lesions becoming detectable. The criteria are identical to those of RECIST v1.1 in many respects but have been adapted to account for instances where an increase in tumor burden, or the appearance of new lesions, does not reflect true tumor progression but rather a favorable inflammation of the tumor.

Unlike RECIST v1.1, iRECIST requires the confirmation of progression on a subsequent scan and uses the terms iUPD (immune unconfirmed progression) and iCPD (immune confirmed progression). Confirmatory scans should be performed at least 4 weeks, but no longer than 8 weeks after iUPD.

For target lesions, iCR, iPR, and iSD can all be assigned after iUPD has been documented, as long as iCPD was not confirmed (Table 9). iUPD is defined by RECIST v1.1 criteria for progressive disease; iUPD can be assigned multiple times as long as iCPD is not confirmed at the next assessment. Progression is confirmed in the target lesion category if the next imaging assessment after iUPD (4–8 weeks later) confirms a further increase in sum of measures of target disease from iUPD, with an increase of at least 5 mm. However, the criteria for iCPD (after iUPD) are not considered to have been met if CR, PR, or SD criteria (compared with baseline and as defined by RECIST v1.1) are met at the next assessment after iUPD. The status is reset (unlike RECIST v1.1, in which any progression precludes later CR, PR, or SD). iCR, iPR, or iSD should then be assigned; and if no change is detected, then the timepoint response is iUPD.

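### Section 8.3.6 gives conflicting instructions for symptoms at an unconfirmed progression, so some non-serious inflammatory symptoms can be left out of the primary adverse-event incidence

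*Combined protocol and SAP*

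**What the plan says.** Incidence of adverse events (AEs), overall and by severity and relationship, is a primary endpoint (Section 3). Section 8.3.6 governs symptoms of the malignancy with three sentences:

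1. Excluded: signs or symptoms "are not reported as AEs if they are clearly consistent with the suspected progression of the underlying malignancy".
2. Optional: symptoms of progression "may be reported as AEs if the symptom cannot be determined as exclusively due to the progression of the underlying malignancy", or if they do not fit the expected pattern.
3. Expected: "If there is any uncertainty about an AE being due only to the disease under study, it should be reported as an AE or SAE".

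For serious events the section is firmer. Events of unclear cause are to be reported within 24 hours, and an "SAE that has been reported should not be deleted from the database if the event is determined to be associated with disease progression".

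Section 4.1.2.2 and the synopsis allow for pseudo-progression. They call progression suspected when it is initially documented, and leave it open until a scan at least 4 and at most 8 weeks later. Appendix 6 (Section 10.6) explains that an apparent increase in tumour burden may be one that "does not reflect true tumor progression but rather a favorable inflammation of the tumor". If a later assessment shows response or stable disease, the status is reset and the iUPD date is not used for iPFS. Table 4 (Section 8.3.1) collects non-serious AEs from first dose until 30 days after the last dose, or until new anticancer therapy if that comes first.

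**The concern.** The word that triggers exclusion from the AE data is the word the protocol uses for a state that may be an effect of SUPLEXA. Pain or swelling at a lesion that looks larger on a scan fits suspected progression, whether the cause is tumour growth or inflammation. Two sites following Section 8.3.6 in good faith can therefore handle the same symptom differently.

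This is a first-in-human study, and AE incidence by relationship is part of its primary objective. Section 4.3 also relies on the absence of treatment-related events to support the later dosing, so a few unrecorded events would matter.

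**Working it through.** No formula in the plan governs this rule. The check sets the passages side by side and then gives a scale.

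**Step 1: a non-serious symptom at iUPD under each sentence of Section 8.3.6.**

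| Sentence | Condition | Instruction |
|---|---|---|
| First | Clearly consistent with suspected progression | Not reported |
| Middle | Cannot be determined as exclusively due to progression | *May* be reported |
| Last | Any uncertainty that it is due only to the disease | *Should* be reported |

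In the first sentence, *clearly* qualifies the fit between symptom and suspicion. It does not require the progression to be real. The middle and last conditions describe essentially the same symptoms: one that cannot be put down exclusively to progression is one whose cause is uncertain. One sentence makes reporting optional and the other expects it.

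**Step 2: after the confirming scan.** On the efficacy side, Section 10.6 resets the status and discards the iUPD date. On the safety side, neither Section 8.3.6, Section 8.3.3 nor Appendix 3 tells the site to go back and enter a symptom it withheld.

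**Step 3: timing.** Take a subject whose last dose is at or before the iUPD. AE collection closes no later than 30 days after that iUPD. The confirming scan comes 4 × 7 = 28 to 8 × 7 = 56 days after it. Apart from scans on days 28 to 30, the answer arrives after collection has closed. A symptom with onset inside the window could be entered later, but no text asks for that.

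**Step 4: what other rules already cover.**

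- Serious events of unclear cause: Section 8.3.6.
- Events resulting in death: Section 8.3.7. Section 10.3.2 gives death from progression as an example that is not an SAE, a separate mismatch to reconcile.
- Events more severe than expected for the subject: Section 10.3.1.

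What remains exposed is non-serious, non-fatal symptoms of expected severity. They arise in the solid-tumour cohort, because iRECIST applies only there.

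**Step 5: scale.** Section 9.1 plans approximately 60 subjects. If all are treated, the Safety Analysis Set is 60. Overall incidence counts subjects, so one subject whose only AE is withheld lowers it by 1/60 = 0.0167, or about 1.7 percentage points. A subject with any other recorded AE still counts, and overall incidence does not change. Treatment-related incidence is more exposed. Section 2.3.1 reports no treatment-related events in more than 15 subjects as of September 2022, so such a subject is unlikely to have a second related event that keeps them in the count.

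**The case against.** The strongest answer is the closing sentence of Section 8.3.6. At iUPD the cause is open on the protocol's own account, so there is uncertainty and the symptom should be reported. On this view the first sentence covers only clear cases and there is no conflict. Much of this stands: read literally, the last sentence captures these symptoms. It does not dispose of the point. The middle sentence still makes reporting optional for the same symptoms, iUPD is not mentioned, and the first sentence sets its threshold at suspicion.

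The collection window also limits the reach. A subject given only three doses has the last one 14 days after the first, so non-serious AE collection ends at 14 + 30 = 44 days, or 44/7 = 6.3 weeks. The first scan is due at Week 6 to 12, so most first iUPDs in such subjects fall outside collection anyway. That stands. The exposure lies mainly in subjects who continue dosing.

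A reader might also infer that the dose-limiting-toxicity exemption for a "Grade 3 inflammatory reaction attributed to a local anti-tumour response" leaves the AE table as the only place such events could appear. The documents do not support this:

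- The DLT periods end before the third dose, well before the first scheduled scan.
- The exemption concerns reactions attributed to an anti-tumour response, not symptoms attributed to progression.
- Related immunological events of Grade 3 or above also count under Sections 7.1 and 7.2.

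**Conclusion.** Section 8.3.6 is inconsistent for symptoms arising at an unconfirmed progression, and nothing revisits the decision if progression is not confirmed. Non-serious, non-fatal inflammatory symptoms in solid-tumour subjects can be left out of the primary AE incidence at sites that apply the first sentence alone.

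A reader might go further and conclude that real treatment effects do drop out of the AE data. That is not established, because a site following the closing sentence would record them.

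Nor can a total under-count be given. The documents state no rate of pseudo-progression or of symptoms during it. Any total would rest on an assumed rate, and on every case being symptomatic, withheld and free of any other AE. The figure of about 1.7 percentage points per affected subject assumes 60 treated subjects and that the withheld event was the subject's only AE.

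**What to change.** Make two changes in Section 8.3.6.

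1. In the middle sentence, replace *may be reported* with *must be reported*, so that it agrees with the closing sentence.
2. Add a rule along these lines: *In the solid-tumour cohort, a symptom arising at an unconfirmed progression (iUPD) within the AE collection period counts as uncertain and is entered as an AE, with grade and causality, when it occurs. If progression is later confirmed, the entry is flagged as progression-associated and kept. If it is not confirmed, causality is re-assessed.*

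The cost is a short wording change, one eCRF flag, somewhat more AE entries and a slightly less favourable AE incidence.

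There is no need to require confirmed progression before any symptom may be excluded. That would turn ordinary progression symptoms into AEs whenever no confirming scan is done, for example after a subject starts new therapy and leaves the study. For the haematologic cohort the documents define no criterion of confirmed progression on which such a rule could rest; Section 8.1.2 refers only to standard of care.

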### **8.3.7 Death Events**

All death events will require completion of a death data collection page within the eCRF.

Timelines for reporting of death events are identical to the requirements for SAE reporting. (Appendix 3, Section 10.3). Events resulting in death will be an SAE regardless of association to disease progression (Section 8.3.6). Death is an outcome and should not be reported as an event term. The event that leads to the death should be reported as the SAE term.

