### Events NOT Meeting the AE Definition

- Any clinically significant abnormal laboratory findings or other abnormal safety assessments which are associated with the underlying disease, unless judged by the Investigator to be more severe than expected for the subject's condition.
- The disease/disorder being studied or expected progression, signs, or symptoms of the disease/disorder being studied, unless more severe than expected for the subject's condition.
- Medical or surgical procedure (e.g., endoscopy, appendectomy): the condition that leads to the procedure is the AE.
- Situations in which an untoward medical occurrence did not occur (social and/or convenience admission to a hospital).
- Anticipated day-to-day fluctuations of pre-existing disease(s) or condition(s) present or detected at the start of the study that do not worsen.

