### 10.3.2 Definition of SAE

If an event is not an AE per definition above, then it cannot be an SAE even if serious conditions are met (e.g., hospitalization for signs/symptoms of the disease under study, death due to progression of disease).

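### Deaths clearly due to progression are SAEs under Section 8.3.7 but cannot be SAEs under Sections 10.3.1 and 10.3.2, so the primary SAE incidence depends on which section a site follows

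*Combined protocol and SAP*

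**What the plan says.** Section 3 makes the incidence of AEs and SAEs, overall and by relationship, part of the primary endpoint. Section 9.3.3 summarises SAEs descriptively in the Safety Analysis Set and has no rule for fatal progression.

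On fatal events, Section 8.3.7 states: "Events resulting in death will be an SAE regardless of association to disease progression". It adds that the event leading to death supplies the SAE term, and that every death needs its own eCRF page. It cites Section 8.3.6 on progression, and it cites Appendix 3 for reporting timelines.

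On definitions, Section 8.3 states: "The definitions of adverse events (AEs) and serious adverse events (SAEs) can be found in Appendix 3". In that appendix, the Section 10.3.1 list of events that are not AEs includes: "The disease/disorder being studied or expected progression, signs, or symptoms of the disease/disorder being studied, unless more severe than expected". Section 10.3.2 then says that an event failing the AE definition "cannot be an SAE even if serious conditions are met (e.g., hospitalization for signs/symptoms of the disease under study, death due to progression" of disease.

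On the collection period, Section 8.3.1 opens with: "All AEs and SAEs will be collected from the signing of the ICF until the follow-up visit". That sentence goes on to refer to the Schedule of Activities (SoA) for the time points, and the next one introduces Table 4. Table 4 collects AEs from first dose "until 30 days after the last dose of study intervention discontinued or before initiation of subsequent anticancer therapies, whichever comes first". Its SAE entry reads "From consent until 30 days after the last dose of study intervention discontinued for all SAEs", with only related SAEs after that. The AE note in the SoA limits collection to related SAEs in what reads as the follow-up period.

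**The concern.** The same event, a death clearly due to progression, must be recorded as an SAE under Section 8.3.7 and cannot be one under Section 10.3.2. A site cannot comply with both. If sites differ, the pooled SAE incidence is a mixture of two definitions, in proportions that reflect site practice rather than the product.

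Such deaths can arise inside the collection window. Section 4.1.2.2 lets subjects continue dosing after RECIST v1.1 progression at the investigator's discretion, so a subject with progressing disease may die within 30 days of a dose.

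The SAP can choose how to tabulate, but it does not change what sites were told to enter. The study is open-label, and Section 9.3 requires the SAP only before database lock. Unless a rule is fixed now, the choice could be made after the deaths are known.

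**Working it through.** **Step 1. Can the passages be read together?** The protocol states no figure on this point, so the check begins with the text.

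| Reading that might reconcile them | Result |
|---|---|
| Section 8.3.7 is an exception to the general rule | It cites Section 8.3.6 and reads as an exception to that section. It cites Appendix 3 only for timelines, and nothing makes it an exception to the definitions there. |
| A fatal outcome is more severe than expected, so the exemption in Section 10.3.1 applies | Section 10.3.2 names death from progression as a non-SAE, so the exemption cannot cover the clear cases. |
| Death is one of the seriousness criteria | Section 10.3.2 applies its AE test first. A non-AE fails even when a seriousness criterion is met. |

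None of the three resolves the conflict.

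**Step 2. Which deaths are affected?** Only those clearly due to progression. Section 8.3.6 has uncertain cases reported, and Section 10.3.1 brings back events more severe than expected. These deaths would normally be judged unrelated. Table 4 stops collecting unrelated SAEs 30 days after the last dose, so the affected deaths are those up to that point.

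**Step 3. Size.** Inputs:
- n = 60, the approximate planned enrolment in Section 9.1, taking all as dosed (the Safety Analysis Set in Section 9.2 requires at least one dose).
- s = subjects with some other SAE.
- f = subjects whose only SAE would be a progression death in the window. The documents do not give f.
- k = those of the f subjects treated at sites that follow Section 8.3.7, so 0 ≤ k ≤ f.

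Incidence under Section 10.3.2 everywhere = s/n.
Incidence under Section 8.3.7 everywhere = (s + f)/n.
Incidence with mixed practice = (s + k)/n, somewhere between the two.

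The difference between the two rules is f/n, whatever s is. Per death: 1/60 = 1.67 percentage points.

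For scale only, with f assumed: f = 1 gives 1/60 = 1.7 points, f = 3 gives 3/60 = 5.0 points, and f = 6 gives 6/60 = 10.0 points. These totals are not forecasts.

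**Step 4. What does not move?** Section 6.5 already excludes from DLTs any AE reasonably attributed to progression. The death rule in Section 7.1 applies only to deaths not due to progression. Related-SAE incidence changes little, because these deaths would normally be judged unrelated.

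**The case against.** The strongest reply is that this is a wording inconsistency with little reach. Nothing is tested, and the safety analysis is descriptive. Section 8.3.7 requires a death page for every death, on SAE timelines, so the sponsor can find each death that has no matching SAE and retabulate. Solid-tumour subjects with ECOG status 2 or worse, and all subjects with a life expectancy under 6 months, are excluded, which makes many early progression deaths less likely. All of this stands and limits the consequence. It does not remove the contradiction, because someone must still choose the rule that the retabulation follows.

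A reader might infer three stronger points that the documents do not support.

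- *That the error is locked into the data.* Section 8.3.6 says "SAE that has been reported should not be deleted from the database if the event is determined to be associated with disease progression" on later workup. In context, that sentence concerns events whose cause was unclear at onset, whereas the conflict here concerns deaths clearly due to progression. With the death page as well, the data can be corrected.
- *That Section 8.3.1 extends collection of unrelated SAEs through the 8-weekly follow-up visits.* Its first sentence is loosely worded, but it defers to the SoA, whose AE note limits collection to related SAEs in what reads as follow-up, and it leads straight into Table 4. Read together, these support the 30-day limit for unrelated SAEs. What remains is an editorial mismatch, so no extra collection time should be claimed.
- *That incidence would shift by 5 or 10 points.* Those totals need assumed numbers of deaths. Only the amount per death follows from the documents.

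**Conclusion.** The concern holds for one class of event: deaths clearly due to progression, within 30 days of the last dose. Section 8.3.7 counts them as SAEs, Sections 10.3.1 and 10.3.2 do not, and no precedence is stated. SAE incidence, part of the primary endpoint, therefore has two possible values from the same clinical events.

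The size is 1.67 percentage points per death. This assumes 60 dosed subjects and that the death is the subject's only SAE; with fewer dosed subjects, each death counts for more. The total cannot be derived. The point is worth correcting because the endpoint is primary and the correction is cheap, but it does not threaten the trial's safety conclusions.

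**What to change.** Reconcile Section 8.3.7 with Sections 10.3.1 and 10.3.2 to one rule before further data are pooled. Either of these would do:

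1. **Keep the Section 8.3.7 rule.** Add an exception for events with a fatal outcome, cross-referring to Section 8.3.7, to the progression bullet in Section 10.3.1 and to the non-AE clause in Section 10.3.2. Delete the progression-death example from that clause.
2. **Keep the Section 10.3.2 rule.** Limit Section 8.3.7 to fatal events not due solely to progression.

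Under either option, report one summary line giving SAE incidence with and without events due solely to progression. Where sites have already followed different rules, the death pages can be used to bring the entries into line.

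As an editorial clean-up only, replace the first sentence of Section 8.3.1 with the Table 4 periods and align the AE note in the SoA with them.

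The cost is a few sentences of protocol text and one line in a table, with no new data collection. The downside of option 1 is that the headline SAE incidence may be higher.
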